9.2 Confinement and Washout

In Part 1 of the study (SAD), subjects in Cohorts 1 to 4 will be confined from the morning of Day -1 until Day 4 (after the 72-hour post-dose blood draw).

Cohort 5 subjects will be confined from the morning of Day -1 until Day 3 (after the 48-hour post-dose blood draw). Subjects will come back to the clinic on Day 4 for the final blood draw and safety procedures at the Study Exit visit.

There will be a washout period of at least 7 days between each administration of the IP in Part 1 of the study and between Parts 1 and 2 of the study.

In Part 2 of the study (MAD), Cohort 6 subjects will be confined from the morning of Day -1 until Day 16 (after the 72-hour post-last dose blood draw). Subjects will come back on Day 17 for the subsequent final blood draw (96-hour post-last dose blood draw) Study Exit visit.

Participation of each subject in this study should last approximately 2½ weeks excluding the time needed for the screening visit.

9.2.1 Outings

Given the long confinement of the study, outings will be permitted during the confinement. Pre-scheduled and supervised outings will also be permitted for smoking subjects during confinements.

Outings will be supervised at all times by the clinical staff to ensure compliance with protocol and will be limited to the grounds surrounding the clinic, as per the clinical site-specific procedures for supervised outings.

9.3 Randomization and Blinding

This study will be open-label due to the objective nature of the data.

Cohorts 1 to 4 (Part 1, SAD) and 6 (Part 2, MAD) will each include the following groups of hepatic-impaired subjects:

- Group 1: Child-Pugh Group A: score 5-6 points; 6-8 subjects with mild hepatic impairment
- Group 2: Child-Pugh Group B: score 7-9 points; 6-8 subjects with moderate hepatic impairment
- Group 3 (Part 1, SAD only): Child-Pugh Group C: score 10-15 points; 4-6 subjects with severe hepatic impairment

Cohort 5 (Part 1, SAD) will include 6-8 healthy subjects with normal hepatic function (control group).

An effort will be made to carefully match the healthy subjects (Cohort 5, SAD) with the subjects with mild and moderate hepatic impairment (Cohorts 1 to 4, SAD) by age (± 10 years), BMI ($\pm 15\%$), and gender, to the extent possible. Matching strategy will enroll control subjects with normal hepatic function to meet demographically matched mean criteria of the pooled subjects with mild and moderate hepatic impairment.

9.4 Investigational Product (IP)

The Investigational Product (IP) NAL ER tablets (4 strengths) will be supplied by the Sponsor. NAL ER tablets, 27 mg and 54 mg, are white to off-white film coated round tablets (7.9 mm). The NAL ER tablets 108 mg (7.6×15.7 mm) and 162 mg (9.3×15.4 mm) are white to off-white film coated oblong tablet. NAL ER tablets will be shipped to the Pharmacy packaged in 70 count HDPE bottles with an induction inner seal and child-resistant (CR) closures.

In Part 1 of the study (SAD), hepatic impaired subjects will receive single ascending oral doses and healthy subjects will receive a single oral dose, under fasting conditions, of NAL ER, at the following dose levels:

Cohort	Planned Dose of NAL ER
1	27 mg
2	54 mg
3	108 mg
4	162 mg
5 (healthy subjects)	Up to 162 mg

For Cohort 1, a minimum of 6 subjects from Group 1 (mild impairment), 6 subjects from Group 2 (moderate impairment), and 4 subjects from Group 3 (severe impairment) will receive a single dose of NAL ER.

For Cohorts 2-5, a minimum of 6 subjects from Group 1 (mild impairment) and 6 subjects from Group 2 (moderate impairment) will receive a single dose of NAL ER.

Cohorts will be dosed sequentially in an ascending design. Enrollment of subjects with mild impairment and moderate impairment can be done in parallel. Subjects with severe impairment will be enrolled upon completion of the highest dose level in mild and moderate impairment subjects. There will be at least 7 days between dosing of each dose level, within the same group of impairment (mild and moderate). Subjects will be observed for a period of 4 days.

Safety, tolerability, and combined mild and moderate impaired subject data will be evaluated by a Safety Committee at the completion of each cohort dose level before proceeding to the next cohort dose level. Therefore, the highest dose administered may be lower than 162 mg. Depending on safety and tolerability, the dose escalation scheme may be modified such that intermediate dose levels are administered.

Based on the overall safety and tolerability observed in the subjects with mild and moderate impairment, at the completion of all doses tested, it will be determined by the Safety Committee whether or not it is safe to proceed with dosing for the first 2 subjects with severe Impairment. After review of the safety and tolerability for the first 2 severe subjects dosed at 27 mg, it will be determined whether or not to complete that dose level for the remaining severe subjects.

At the completion of all subjects dosed in the cohort, there will be an evaluation of safety and tolerability to determine whether to proceed to the next dose level for this group.

The Safety Committee will be composed of at least the Investigators and one medically qualified Sponsor representative. Some adjustments to the currently outlined doses and/or dosing regimen may be implemented by the Safety Committee, but the dose to be administered in a given dose cohort will not exceed the one currently outlined in the protocol.

Drug administration in Part 2 of the study (MAD) may be initiated following satisfactory review of the safety and tolerability data from Groups 1 and 2 (mild and moderate impairment) from Part 1 of the study (SAD) by the Safety Committee. Depending on safety and tolerability as well as on available PK data, the dose escalation scheme may be modified such that intermediate dose levels are administered. The dosage regimen (once daily versus twice daily) will be confirmed following review of PK data from Part 1 of the study (SAD).

If in the judgement of the Safety Committee the Part 1 PK data demonstrates dose linearity across the dose range in both the mild and moderate hepatic impairment subjects (Group 1 and Group 2 subjects), such that PK modeling can be predictive of steady state dosing levels, a decision may be made to end the study without conducting Part 2 of the study

In Part 2 of the study (MAD), subjects will receive a single 27 mg dose in the morning of Day 1. Starting on Day 2, doses will be subsequently escalated for each subject to twice daily, 12 hours apart, 27 mg, 54 mg, 108 mg, and 162 mg over 13 days. On the last treatment day, (Day 13), subjects will receive a single 162 mg dose in the morning. Subjects will remain at each dose level for 2-3 days (minimum 5 consecutive doses) with dose escalation predicated on tolerability of the prior dose (See Section [9.14.4](#) for dose escalation stopping rules).

In Part 2 of the study (MAD), tablets will be administered as indicated in the following titration schedule:

Study Day	Dose (mg)	
	AM	PM
1	27	0
2	27	27
3	27	27
4	27	54
5	54	54
6	54	54
7	54	108
8	108	108
9	108	108
10	108	162
11	162	162

12	162	162
13	162	—
14	—	—
15	—	—
16	—	—

9.5 Drug Supplies and Accountability

It is the responsibility of the Sponsor to ensure that Investigational Product (IP) provided for this study are manufactured under Good Manufacturing Practices (GMP) and are suitable for human use. It is the responsibility of the Sponsor to ship a sufficient amount of IP to the clinical sites to conduct the study. The IP will be stored by the clinical sites per the labeled storage conditions.

Labels will be provided in appropriate languages as required by the country in which the study is conducted. The content of the labeling will be in accordance with local regulatory specifications and requirements. The IP will be stored in a locked, environmentally-controlled medication room with restricted access. Additional instructions for drug dispensing will be provided in a pharmacy manual.

All IP received at the site will be inventoried and accounted for throughout the study and the result recorded in the drug accountability/retention record. The Investigator must maintain accurate records of the receipt of all IP shipped by the Sponsor, or their representative, including but not limited to the date received, lot number, expiration date, amount received, and the disposition of all the IP. Upon completion of the study, all remaining IP will be returned to the depot for destruction.

9.6 Drug Administrations

In Part 1 of the study (SAD), IP will be administered in the morning to each subject with 240 mL of water; and a hand and mouth check will be performed to ensure consumption of the IP. Tablets should be swallowed whole without chewing or crushing.

In Part 2 of the study (MAD), IP will be administered in the morning on Day 1 and the morning and evening starting on Day 2, 12 hours apart (when applicable) to each subject with 240 mL of water and a hand and mouth check will be performed to ensure consumption of the IP. Tablets should be swallowed whole without chewing or crushing.

The tablets should be taken at approximately the same time each day and within 12 hours. A time window of ± 10 minutes from the scheduled dosing time will be allowed. Any deviation in IP administration that is greater than the allowed time window will be considered as protocol deviation. For every dosing day, both the planned and exact dosing times will be documented. Time of dosing will be set as the time the first tablet is administered.

9.7 Study Restrictions

9.7.1 Food and Fluids

In Part 1 of the study (SAD), no food will be allowed from at least 8 hours before NAL ER dosing until at least 2 hours after. A standardized breakfast will be served at least 2 hours after NAL ER dosing. A lunch, supper, and a light snack will be served at appropriate times thereafter. Except for water given with NAL ER, no fluids will be allowed from 1 hour before dosing until 1 hour post-NAL ER dose.

In Part 2 of the study (MAD), on Days 1 and 13, no food will be allowed from at least 8 hours before dosing until at least 2 hours after dosing. A standardized breakfast will be served at least 2 hours after NAL ER dosing. For other dosing days, no food will be allowed from at least 2 hours before each dosing until at least 2 hours after dosing. Except for water given with IP, no fluids will be allowed from 1 hour before each dosing until 1 hour post-dose. Water will be provided *ad libitum* at all other times.

In addition, subjects will be required to abstain from:

- Food containing poppy seeds within 24 hours prior to admission and for the duration of the study;
- Food or beverages containing xanthine derivatives or xanthine-related compounds (coffee, black/green tea, chocolate) or energy drinks from 48 hours prior to first dosing until study exit;
- Natural health products (including herbal remedies, homeopathic and traditional medicines, probiotics, food supplements such as vitamins, minerals, amino acids, essential fatty acids, and protein supplements used in sport) from 7 days pre-first dose until study exit unless such products are deemed medically necessary for standard of care by hepatic impaired subjects;
- Food or beverages containing grapefruit, Seville orange, starfruit, pomegranate, pineapple, or pomelo from 14 days prior to first dosing until study exit.

9.7.2 Tobacco, Alcohol, and Illicit Drugs

Subjects will be required to abstain from using soft or hard drugs from screening and throughout the study, and on Day 1, 4, 7, 10, and 13, from smoking from at least 2 hours prior to dosing until 2 hours post-dose and on other dosing days from at least 1 hour prior to dosing until 1 hour post-dose. Subjects will not be allowed to smoke more than 5 cigarettes or equivalent per day.

Consumption of alcohol-based products will be prohibited from 24 hours prior to admission until the study exit.

9.7.3 Concomitant Medications

Cohorts 1 to 4 and 6: Stable medications that are not expected to interfere with the PK of NAL ER will be allowed during the study. No other concomitant drug therapy (prescription or over-the-counter medications) and/or food or beverage outside of the restrictions set out in Section [9.7.1](#) will be allowed during the study except one(s) required for the medical management of an adverse event, a new medical condition, or as allowed by the Safety Committee as discussed in the next

paragraph. Any concomitant medication use at the time of screening, other than the occasional use of acetaminophen, will be evaluated on a case-by-case basis by the Investigator. All concomitant medication use will be documented from screening through study exit/early termination.

In the absence of titration there is a dose response relationship between NAL ER and specific AE frequencies in healthy subjects noted in prior single dose studies, therefore the Safety Committee may determine at any time, using ongoing safety data obtained during the course of the SAD period of the study, whether prophylactic treatment (such as the use of an anti-emetic) will be allowed prior to dosing subsequent subjects.

If a subject is taking an excluded medication, the Investigator can switch the subject to an alternate medication that is allowed and subject can be screened for the study after appropriate stabilization on the new medication. This will be done after the subject signs the consent form.

Cohort 5: Prescription and over-the-counter medications will be prohibited throughout the study. No concomitant drug therapy will be allowed during the study except one(s) required for the medical management of an adverse event. Any concomitant medication use at the time of screening, other than the occasional use of acetaminophen, will be evaluated on a case-by-case basis by the Investigator. All concomitant medication use will be documented from screening through study exit/early termination.

9.7.4 Posture and Physical Activity

Subjects will be allowed to engage in normal activity throughout the study. In Part 1 of the study (SAD), subjects will be required to avoid lying down or sleeping, unless medically necessary or procedurally required, for 4 hours after drug administration. In Part 2 of the study (MAD), on Days 1, 4, 7, 10, and 13, subjects will be required to avoid lying down or sleeping, unless medically necessary or procedurally required, for 4 hours after morning drug administration.

Because excessive physical activity may increase the level of CPK above the upper normal limit value, subjects will be advised to avoid performing such activity at all times during the study duration. Vigorous activity will be prohibited at all times during the confinement.

9.7.5 Other Restrictions

Subjects will be asked not to wear artificial nails or nail polish at screening, and during confinements, at least on the fingers used for pulse oximetry monitoring, in order to avoid false readings.

9.8 PK Sample Collection and Processing

9.8.1 Plasma Samples

Part 1 (SAD) – Cohorts 1 to 5

A total of 11 blood samples will be collected: at pre-dose and 1.5, 3, 5, 7, 9, 12, 24, 36, 48, and 72 hours post-dose (up to 3 mL for each sampling time).

For Part 1, the total volume of blood including that collected for eligibility and safety purposes should not exceed 160 mL for each dose level.

Part 2 (MAD) – Cohort 6

On Day 1: a total of 10 blood samples will be collected for quantitation of nalbuphine and metabolite(s) in plasma: pre-dose and 1.5, 3, 4, 5, 6, 7, 9, 12, and 24 hours post-dose (up to 3 mL for each sampling time).

On Days 4, 7, and 10, a total of 9 blood samples will be collected: at pre-morning dose and 1.5, 3, 4, 5, 6, 7, 9, and 12 hours post-dose (prior to the evening dose administration) (up to 3 mL for each sampling time).

On Day 13, a total of 12 blood samples will be collected: at pre-dose and 1.5, 3, 5, 7, 9, 12, 24, 36, 48, 72, and 96 hours post-last dose (up to 3 mL for each sampling time).

Trough blood samples will be collected on Days 2, 3, 5, 6, 8, 9, 11, 12, and 13 prior to the morning and evening (if applicable) dose administrations (up to 3 mL for each sampling time). Pre-dose samples for the evaluation of steady state attainment will be collected at approximately the same time each day and within 10 minutes prior to dosing.

The 12-hour and 24-hour (when applicable) post-morning Day 1, 4, 7, 10, and Day 13 dose samples will be collected within 10 minutes of the nominal time. For timepoints up to 1 hour, a window of ± 1 minute will be allowed for blood collection. From 1.5 hour to 2 hours, a window of ± 2 minutes will be allowed. From 2.5 hours to 12 hours, the time window will be ± 5 minutes and for 16 hours to 72 hours, the time window will be ± 10 minutes. Actual post-dose sampling times will be used for PK analyses.

Unless otherwise specified or for subject safety, when blood draws and other procedures coincide, blood draws will have precedence. A saline intravenous catheter may be used for blood collection to avoid multiple skin punctures, when appropriate. Otherwise, blood samples will be collected by direct venipuncture.

For Part 2, the total volume of blood including that collected for eligibility and safety purposes should not exceed 358 mL for the whole study.

Plasma samples will be collected and processed as per the Analytical Methodology Information Sheet. Plasma samples will be analyzed to determine nalbuphine and M1, M2, M4, and M5 metabolite concentrations using validated assay methods.

9.9 Pharmacodynamic Assessment

For Part 2 only, WI-NRS measure will be used to determine the severity of itch experienced by subjects with hepatic impairment at screening. Subjects will complete the two WI-NRS forms (the “Nighttime Itch” and the “Daytime Itch”) at the same time during the screening visit and the average will be taken to determine the baseline severity.

For all Cohort 6 subjects, WI-NRS measure will also be performed on a daily basis from Day -1 to Day 16, twice a day, once within an hour of completing their morning and evening meals (if applicable). Subjects will fill in the “Nighttime Itch” form in the morning and the “Daytime Itch” form in the evening.

Please refer to Appendix 1 Section 17 for WI-NRS.

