- Blood pressure, heart rate, and respiratory rate: at screening, in the morning of Day -1, pre-morning dose every day (Days 1 to 13), approximately 1, 2, 4, 6, 8, and 12 hours post-morning dose on Day 1 and Day 13, approximately 2 and 6 hours post-morning dose on Days 2 to 12, and once on Days 14, 15, and 16.
- 12-lead ECG: at screening, in the morning of Day -1, pre-morning dose every day (Days 1 to 13), approximately 1, 2, 4, 6, 8, and 12 hours post-morning dose on Day 1 and Day 13, and once on Days 14, 15, and 16.
- Oxygen saturation via pulse oximetry will be measured at screening. Baseline continuous pulse oximetry will be measured during the nighttime of Day -1 (minimum of 8 hours prior to first dose administration). Following the first dose and throughout study conduct, oxygen saturation will be measured via pulse oximetry at pre-morning dose, at 1.5, 4.5, and 8 hours following the morning dose, and at 2 hours following the evening dose. Pulse oximetry measurements may be collected within 10 min before or after the specified time point. Oxygen saturation will be monitored via pulse continuous oximetry beginning at bedtime and continuing overnight until waking time from Day 1 to end of confinement with oxygen saturation measurements specifically recorded at approximately midnight and 4 am.
- Laboratory assessments (ie, clinical chemistry, hematology, coagulation, and urinalysis) will be done at screening, in the morning of Day -1, and Day 16 following a fasting period of at least 8 hours. Clinical chemistry and hematology also on Day 5 and Day 10.
- Cohort 6 subjects will complete both of the two WI-NRS forms (the “Nighttime Itch” and the “Daytime Itch”) at the same time during the screening visit, and the average will be taken to determine the baseline severity. WI-NRS will be subsequently performed on a daily basis, from Day -1 to Day 16, to be collected twice per day: once within an hour (+/- 1 hour) of completing their morning and evening meals, if applicable. Subjects will fill in the “Nighttime Itch” form in the morning and the “Daytime Itch” form in the evening.
- Cohort 6 subjects will be confined from the morning of Day -1 until discharge on Day 16 (after the 72-hour post-last dose blood draw). Subjects will come back on Day 17 for the subsequent final blood draw (96-hour post-last dose blood draw) at the Study Exit visit.
- PK blood samples:

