17.1 Appendix 1: Worst Itch Numerical Rating Scale (WI-NRS)

The WI-NRS is comprised of one item and represents the numbers 0 (“no itch”) to 10 (“worst imaginable itch”). Subjects are asked to rate the intensity of their itch using this scale.

The time needed for WI-NRS completion is about 1 minute.

Subjects will fill 2 separate forms: One in the morning (“Nighttime Itch”) and the second in the evening (“Daytime Itch”). During the screening visit only, the subject will complete both forms at the same time.

A. To Be Completed by the Subject Each Morning:

NIGHTTIME ITCH: Worst itch experienced from bedtime last night to awakening this morning (ie, worst itch last NIGHT).

Please indicate the severity of the **WORST ITCHING** you experienced by marking the number that best describes it.

Numerical Rating Scale										
0	1	2	3	4	5	6	7	8	9	10
No Itch										Worst Imaginable Itch

B: To Be Completed by the Subject Each Evening:

DAYTIME ITCH: Worst itch experienced from awakening this morning to now (ie, during the DAYTIME).

Please indicate the severity of the **WORST ITCHING** you experienced by marking the number that best describes it.

Numerical Rating Scale											
0	1	2	3	4	5	6	7	8	9	10	
No Itch											Worst Imaginable Itch

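### Tying the itch forms to meals puts the Day 1 Nighttime form after the first open-label dose and leaves the time from the Daytime form to bedtime unrated

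*Protocol*

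**What the plan says.** **When the forms are completed.** Protocol 9.9 and SAP 8.7 ask for the WI-NRS from Day -1 to Day 16, "twice a day, once within an hour of completing their morning and evening meals (if applicable"). The Protocol synopsis, footnote f of Schedules 4.2 and 4.3, and Sections 9.11.1 and 9.11.2 use the same meal link with a wider tolerance where they give the timing: "once within an hour (+/- 1 hour) of completing their morning and evening meals, if applicable". Protocol 9.9 assigns the forms: "Subjects will fill in the “Nighttime Itch” form in the morning and the “Daytime Itch” form in the evening".

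**What the forms ask (Protocol 17.1).** Nighttime: "Worst itch experienced from bedtime last night to awakening this morning". Daytime: "Worst itch experienced from awakening this morning to now".

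**When food is allowed (Protocol 9.7.1).** In Part 2, "on Days 1 and 13, no food will be allowed from at least 8 hours before dosing until at least 2 hours after dosing", and "A standardized breakfast will be served at least 2 hours after NAL ER dosing". In addition, "For other dosing days, no food will be allowed from at least 2 hours before each dosing until at least 2 hours after dosing".

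**Dosing and analysis.** The Part 2 titration table (Protocol 9.4) gives a morning dose only on Day 1 and on Day 13, and morning and evening doses 12 h apart on Days 2-12. Protocol 12.3 compares each itch time point with the pre-dose baseline. SAP 8.7 plans summaries of values and changes from baseline. The one itch baseline that either document describes is the average of the two forms completed at the screening visit, which sets baseline severity.

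**The concern.** The form schedule follows meals, and meals are kept away from doses. Two consequences follow.

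First, subjects are admitted on the morning of Day -1, so the night before Day 1 is the only untreated night that they spend in the clinic during Part 2. The rating of that night is given on Day 1 after breakfast, hence after an open-label dose. The subject then recalls untreated itch while knowing that treatment has started and possibly already feeling it. An analyst who sorts records by time stamp will also find the rating on the post-dose side. For laboratory tests, vital signs and ECG, the SAP takes baseline as the last result before drug administration (7.3, 7.4, 7.6). If that convention were carried over to itch, the last untreated in-clinic night would not count as pre-dose.

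Second, the two recall periods do not meet. The Daytime period closes when the form is filled in, and the Nighttime period opens at bedtime. On Days 2-12 the hours just after the evening dose can fall between them. The first 54, 108 and 162 mg doses are all evening doses (Days 4, 7 and 10). Reducing itch is a secondary objective, Protocol 5.2 speaks of a dose-dependent effect, and unrated hours cannot be recovered in analysis.

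**Working it through.** The plan states no figure for this point, so the check is interval arithmetic on its own timing rules.

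**Inputs from the documents**
- Form within 1 h of finishing the meal (Protocol 9.9, SAP 8.7), with an extra +/- 1 h elsewhere.
- Breakfast at least 2 h after dosing on Days 1 and 13, and no food within 2 h of any other dose (Protocol 9.7.1).
- Evening doses on Days 2-12, which is 11 doses (Protocol 9.4).
- Median Tmax 3-6 h post-dose (Protocol 5.1.1.2), or 2-5 h across the dose levels of the multiple-dose study (Protocol Table 2).

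**Assumed, because the documents do not say**
- Meal length 0.25-1 h.
- Bedtime B = 1-4 h after the evening dose.

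**Step 1. Day 1 Nighttime form, hours after the first dose**
- Earliest completion = 2 + meal length: 2 + 0.25 = 2.25 h to 2 + 1 = 3.0 h.
- If the +/- 1 h window allows completion before the meal ends, subtract 1: 1.25 h to 2.0 h.
- Every reading is post-dose. The recall period ends at awakening, which precedes the dose.

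**Step 2. Evening gap on Days 2-12, with the evening dose at time 0**

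(a) *Meal before the dose.* The meal ends at -2 h or earlier, so under 9.9 the form is completed at -1 h or earlier.
- Whole gap, form at its latest = B - (-1): 1 + 1 = 2 h to 4 + 1 = 5 h.
- Post-dose part of the gap = B: 1 h to 4 h, or 1/12 = 8% to 4/12 = 33% of the dosing interval.
- If the +/- 1 h is read as up to 2 h after the meal, the latest form is at -2 + 2 = 0 h. The whole gap falls to 1-4 h and the post-dose part is unchanged.

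(b) *Meal after the dose.* The meal starts at +2 h. With a 0.25-0.5 h meal and the form completed as it ends, the form is at 2.25-2.5 h. For bedtimes 2.5-4 h post-dose, the unrated time is B - form time.
- Smallest: 2.5 - 2.5 = 0 h.
- Largest: 4 - 2.25 = 1.75 h.

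**Step 3. What is still rated**
- The Nighttime form covers bedtime to awakening, which for most assumed bedtimes includes much of the median Tmax range after the evening dose.
- Days 1 and 13 have no evening dose, so the gap on those days holds no hours just after one.
- Before the first dose there remain both forms at screening and the Day -1 forms. The Day -1 Nighttime form refers to the night before admission.

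**The case against.** The strongest reply has four parts.

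- **Completion time is not recall period.** The Day 1 Nighttime item closes before the dose, so it still rates an untreated night. This stands. A reader might infer that treated itch enters the untreated reference, and the documents do not support that. They nowhere make the Day 1 Nighttime form the baseline; the itch baseline that they describe comes from screening.
- **Other pre-dose ratings exist.** This stands. A reader might infer that Day -1 supplies the only Nighttime form completed on site before dosing, but both forms are also completed at the screening visit.
- **The evening gap rests on meal times that the plan does not give.** This stands as to size. Protocol 9.7.1 permits the evening meal on either side of the dose. A reader might infer a loss of 3-5 h every day (3/24 = 12.5% to 5/24 = 20.8%) from an assumed clock: doses at 08:00 and 20:00, supper over by 18:00, form by 18:00-19:00, bed at 22:00-23:00. That clock is not in the documents. The figure also ignores the +/- 1 h window, which could allow the form at 20:00 and leave 2-3 h. And 1-2 of those hours precede the 20:00 dose, so the post-dose part is again 2-3 h (8-12.5% of 24 h).
- **The plan claims no 24-hour itch endpoint, and form timing is not its main limit.** Each time point is evaluated separately, and Daytime forms follow morning doses at every level. The itch data are open-label and uncontrolled. This lowers the priority. It does not remove the two timing facts, and the words *if applicable* supply no alternative completion time.

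**Conclusion.** Two facts hold on the documents alone. The Day 1 Nighttime form is completed after the first open-label dose, and no form covers the time from the Daytime form to bedtime.

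The first is a matter of recall and classification for one rating per Cohort 6 subject. On days other than 1 and 13, the food rule does not by itself force breakfast after the dose. By Day 13 the rated night is already a treated one, so Day 1 is the case that matters.

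The second affects up to 11 evening doses. The unrated post-dose time is about 1-4 h if the evening meal precedes the dose and about 0-1.75 h if it follows, on assumed bedtimes and meal lengths. Only part of the evening-dose effect is unrated. A bias in the change scores is not shown, since the Day -1 and treatment-day forms share the same meal link and item wording.

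The weight is minor. Itch is a secondary objective, called exploratory in the study title. Part 2 has up to 16 subjects and may not be run. The change is worth making because it is nearly free.

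**What to change.** In the Protocol synopsis, Section 9.9, footnote f of Schedules 4.2 and 4.3, Sections 9.11.1 and 9.11.2, and SAP 8.7:

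1. Have the Nighttime form completed on waking and before the morning dose, where there is one, and record the completion time. The Day 1 rating of the untreated in-clinic night then becomes a true pre-dose value.
2. Reconcile the completion window. The +/- 1 h tolerance is missing from Protocol 9.9 and SAP 8.7.

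Optionally, have the Daytime form completed at bedtime so that the two recall periods meet. This has a real drawback: on Days 4, 7 and 10 the morning and evening doses differ, so one Daytime rating would span two dose levels. A team that prefers ratings tied to a single dose level may reasonably leave the Daytime form where it is and state in the SAP that the interval before bedtime is unrated.

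The cost is wording and a recorded time, with the same two forms of about a minute each in confined subjects. Item wording, dosing and food rules are untouched. Timing may no longer match any previous data collected after meals.
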